### 17.1 General

Continuous data will be presented in terms of evaluable and missing observations, arithmetic mean, standard deviations (SD), median, minimum and maximum value. In addition, for the parameters AUC and  $C_{max}$  the geometric mean and coefficient of variation (CV) will be presented.

Categorical data will be presented as counts and percentages. When applicable, summary data will be presented by treatment, and by assessment time. Individual subject data will be listed by subject number, treatment, and, where applicable, by assessment time.

All descriptive summaries and statistical analyses will be performed using SAS Version 9.4 or later (SAS Institute, Inc., Cary, NC).

Baseline will be defined as the visit with last data collection point prior to the first use of IP.

No imputation of missing data will be performed.

For subject questionnaires measured at each PK time point, the Bonferroni-Holm p-value adjustment will be applied.

### 17.2 Determination of sample size

No formal sample size calculation has been performed for this study. The proposed sample size is considered sufficient to provide adequate information for the study objectives.

Approximately 54 subjects will be screened to achieve 27 randomised subjects.

### 17.3 Analysis data sets

#### 17.3.1 *Full analysis set*

The Full Analysis Set (FAS) will consist of all subjects who have been randomised and used at last one of the IPs and who has at least one post-baseline assessment of data.

#### 17.3.2 *Pharmacokinetic analysis set*

The Pharmacokinetic analysis set (PKAS) will consist of all subjects who used at last one of the IPs and provided an evaluable plasma concentration profile and who have no AEs or protocol deviations judged to affect the PK analysis. Individual PK values may be excluded

from the analysis as specified in the SAP. The PKAS will be used as the per protocol analysis set.

## 17.4 Description of study population

### 17.4.1 *Demographics and baseline characteristics*

Descriptive statistics for demographics, physical examinations, weight and height will be presented by sequence. All data will be listed by subject.

### 17.4.2 *Medical/surgical history and prior/concomitant medication*

Medical/surgical history will be presented by system-organ-class (SOC) and preferred term (PT). Prior/concomitant medications will be presented by ATC level 3 and 5.

Medical/surgical history and prior medications will be presented overall by descriptive statistics and listings. Concomitant medications will be presented by sequence.

All data will be listed by subject.

### 17.4.3 *Treatment compliance*

The number of subjects treated in sequence and their individual IP use will be listed.

## 17.5 Analysis of primary endpoints

### 17.5.1 *Analysis of pharmacokinetics*

The PK analysis will be based on the PK analysis set and performed by CTC. The PK parameters will be calculated by non-compartmental analysis (NCA) using the software Phoenix WinNonlin® version 8.1 or later (Certara, U.S.A.).

The following non-compartmental PK parameters will be determined for each IP use:

- $AUC_{\text{inf}}$  (baseline adjusted [when possible] and non-baseline adjusted)
- $AUC_t$  (baseline adjusted [when possible] and non-baseline adjusted)
- $AUC_{0-90}$  (baseline adjusted [when possible] and non-baseline adjusted)
- $C_{\text{max}}$  (baseline adjusted [when possible] and non-baseline adjusted)
- $C_{\text{last}}$  (baseline adjusted [when possible] and non-baseline adjusted)
- $T_{\text{max}}$  (baseline adjusted [when possible] and non-baseline adjusted)
- $T_{1/2}$  (baseline adjusted [when possible] and non-baseline adjusted)

The elimination rate constant,  $\text{Lambda}_z$  (with acceptance criteria;  $R^2$ , extrapolated AUC) will be calculated to support baseline adjustment of above PK parameters.

$C_{\text{max}}$  and  $T_{\text{max}}$  will be derived from the observed plasma concentration data. The AUC will be calculated using log-linear trapezoidal interpolation (linear - up, log - down). Calculations will be based on the actual sampling times recorded during the study. Concentrations below Lower limit of quantification (LLOQ) occurring before  $C_{\text{max}}$  will be treated as zero.

Concentrations below LLOQ occurring after  $C_{\text{max}}$  will be omitted from the analysis.  $AUC_t$ , and  $C_{\text{max}}$  will be corrected for and calculated with and without nicotine baseline corrections. Where plasma nicotine concentrations are above the lower limit of quantification immediately

prior to product use (-5 minutes), PK parameters will be calculated from baseline adjusted concentrations using subjects' elimination rate constant.

Summary statistics for the PK parameters will be presented by product with number of measurements, arithmetic mean, SD, CV, median, minimum, maximum, geometric mean, geometric CV%. All data will be listed by subject.

The primary objective will be examined by the following statistical comparisons for  $AUC_t$  and  $C_{max}$ :

- Product A versus Product B, C and D, respectively
- Product B versus Product C and D, respectively
- Product C versus Product D

Log transformed nicotine  $C_{max}$  and  $AUC_t$  estimates will be evaluated separately in a linear mixed-effects analysis of variance model with fixed effects for period, sequence, and product, and a random effect for subject. If the assumptions for this model will be inappropriate will the fixed effects period and sequence be removed from the model. The above product differences will be back-transformed to present the ratios of geometric least squares (LS) means and 95% CIs of each test product versus each other from the same model.

## 17.6 Analysis of secondary endpoints

### 17.6.1 *Pharmacokinetics*

Refer to section 17.5.1.

### 17.6.2 *In vivo extracted amount of nicotine*

The data needed for the analysis of in vivo extracted amount of nicotine are the individual data of amount of nicotine for unused reference pouches and the amount of nicotine left in the study pouches. The mean nicotine concentration of the reference pouch and weight of each individual study pouch and residual nicotine amount will be used to calculate the extracted amount. The mean of extracted amount (mg/unit) and extraction fraction (%) of nicotine for each IP pouch, will be calculated. The orally extracted dose of nicotine will be analysed using the signed Wilcoxon rank sum test for within subject difference (i.e. between IPs). Amount of nicotine in reference pouches and in used pouches will be presented through descriptive statistics. All data will be listed by subject.

### 17.6.3 *Product evaluation scale*

Each question of the PES will be answered using a 7-point Likert scale. Responses will be presented as the following factor scores: 1 = not at all, 2 = very little, 3 = a little, 4 = moderately, 5 = a lot, 6 = quite a lot, 7 = extremely

Four multi-item subscales will be derived from "Satisfaction" (items 1, 2, 3, and 12); "Psychological Reward" (items 4 through 8); "Aversion" (items 9, 10, 16, and 18); and "Relief" (items 11, 13, 14, 15, and reversed for item 20) and single items 17, 19, and 21 will be summarized.

The total score of PES and the sub-scales will be calculated for each product and intraindividual difference for each timepoint assessed will be analysed using a Wilcoxon Signed Rank Sum test.

Data will be presented using descriptive statistics. Subscales will be tabulated by study product and overall at applicable timepoints.

All data will be listed by subject.

#### 17.6.4 *Product preference scale*

The PPS will be presented using a frequency table with number of observations and all combinations of the subject's preference.

All data will be listed by subject.

#### 17.6.5 *Urge to use questionnaire*

The following parameters will be calculated for the urge to use assessments:

$E_{\max}$	The maximum change from baseline VAS score ( $VAS_{\text{pre-use}} - VAS_{\text{post-use}}$ ).
$T_{E_{\max}}$	Time of the $E_{\max}$ . If the maximum value occurs at more than one time point, $T_{E_{\max}}$ will be defined as the first time point with this value.
$AUEC_{0-120}$	The area under the change from baseline VAS score versus time curve from time 0 to 120 minutes, calculated using the linear trapezoidal method with linear interpolation using actual sample times.

Responses and derived parameters will be summarized by IP and overall using descriptive statistics.

An appropriate statistical method, similar to the PK analysis detailed in Section 17.5.1 will be used to compare Urge to Smoke parameters (no data transformation).

All data will be listed by subject.

#### 17.6.6 *Adverse events*

An overview of all AEs, including SAEs, intensity, relationship to IP, and deaths will be presented. Incidence of AEs and SAEs will be summarised by SOC and PT by IP and overall.

All AE data will be listed by subject and include the verbatim term entered by the Investigator.

#### 17.6.7 *Clinical laboratory analyses*

Clinical laboratory data will be summarised by IP with absolute and percent change from baseline.

All data will be listed by subject.

#### 17.6.8 *Vital signs*

Vital signs (systolic/diastolic blood pressure and pulse) will be summarised by IP. Data will be presented with absolute and percent change from baseline.

All data will be listed by subject.

#### 17.6.9 12-lead ECG

All ECGs will be categorised as "normal", "abnormal, not clinically significant", or "abnormal, clinically significant" (as judged by the Investigator) and summarised by IP using frequency tables.

All data will be listed by subject.

2 VERSION HISTORY

This statistical analysis plan (SAP) for study IB-OND-ZONEX-11 is based on the protocol dated 21JUN2021.

Table 1 SAP version history summary

SAP version	Approval Date	Changes	Rationale
0.1	08NOV2021	-	Version ready for internal review
0.2	10NOV2021		Version ready for Sponsor review
1	23NOV2021	NA	Original version

3 INTRODUCTION

This SAP gives details regarding the statistical analyses and data presentation outlined in the final clinical study protocol (CSP) for the study IB-OND-ZONEX-11. Any changes from the final CSP are given in Section 9.

4 CLINICAL STUDY DETAILS

4.1 Clinical study objectives and endpoints

Table 2 Clinical study objectives and endpoints

Objectives	Estimands/Endpoints
Primary	
1. To evaluate and compare the maximum plasma concentration (C_{max}) and the area under the curve at the last timepoint measured (AUC_t) of nicotine after the use of each product.	1.1 C_{max} and AUC_t
Secondary	
2.1 To evaluate other PK parameters of nicotine after the use of each product.	2.1.1 AUC timepoint 0 to 90 minutes (AUC_{0-90}), AUC timepoint 0 to infinity (AUC_{inf}), time to C_{max} (T_{max}), plasma concentration at last timepoint measured (C_{last}), and terminal elimination half-life ($T_{1/2}$).
2.2 To evaluate orally extracted dose of nicotine in used products (oral nicotine delivery [OND]).	2.2.1 The orally extracted dose of nicotine from each pouch will be calculated to evaluate the correlation between baseline-

CONFIDENTIAL

Document name: IB-OND-ZONEX-11_SAP_v1.0_23NOV2021

[figure not shown]
	adjusted AUC _{inf} and orally extracted dose of nicotine.
2.3 To evaluate product perception and preference by use of subjective assessments.	2.3.1 Subjective assessment endpoints including: Product evaluation scale (PES), Product preference scale (PPS) and the Urge to use questionnaire.
2.4 To evaluate the tolerability and safety of each of the products used.	2.4.1 Frequency, intensity and seriousness of adverse events (AEs). 2.4.2 Clinically significant changes in laboratory parameters, vital signs and electrocardiogram (ECG).
Tertiary/Exploratory	
NA	NA

4.2 Clinical study design

This will be a randomised, cross-over, single-blind, confinement study conducted in 27 male or female snus or nicotine pouch users. The study will investigate 4 different nicotine containing products in a cross-over design, incorporating pharmacokinetic (PK) evaluation, nicotine extraction evaluation, subjective questionnaire assessments as well as safety and tolerability evaluation.

During the study participation, subjects will come for 2 visits to the clinic, including a screening visit and a 4-day confinement period. A final follow up end-of-study telephone call will be performed within a week of last product use.

The following figure gives an overview of the study design:

4.3 Statistical hypotheses

4.3.1 Statistical hypotheses related to primary objective

The main statistical hypothesis that will be tested in the study is that AUC_t and C_{max} does not significantly differ for test product A-B [REDACTED] respectively in comparison to product D [REDACTED] I.e., the primary objective will be examined by the following statistical comparisons for AUC_t and C_{max} :

- Product A does not significantly differ from Product D
- Product B does not significantly differ from Product D
- Product C does not significantly differ from Product D

More information about the statistical tests to be performed can be found in Section 8.1.

4.4 Number of subjects

Approximately 54 subjects will be screened to achieve a total of 27 randomised subjects.

4.5 Randomisation

On Day 1, subjects will be randomised to one of 4 treatment sequences. The 4 different products are:

- A: ZoneX [REDACTED] nicotine/pouch
- B: ZoneX [REDACTED] nicotine/pouch
- C: ZoneX [REDACTED] nicotine/pouch
- D: [REDACTED] nicotine/ pouch (comparator product)

The 4 randomisation sequences are described in the table below:

Sequence	Order			
Sequence 1	A	B	C	D
Sequence 2	B	C	D	A
Sequence 3	C	D	A	B
Sequence 4	D	A	B	C

A computer-generated randomisation list will be created by CTC using SAS Proc Plan, SAS Version 9.4 (or later). The randomisation list will contain subject number, sequence and treatment and will be kept by the randomiser until database lock. A copy of the randomization list will be provided to the research clinic.

4.6 Blinding

This is a single-blind study, i.e., the Investigator and study staff, but not the subjects, will know the identity of each IP.

CONFIDENTIAL

Document name: IB-OND-ZONEX-11_SAP_v1.0_23NOV2021

The IP:s differ somewhat in size but are otherwise identical in appearance. The subjects will not know the strength/nicotine content of each IP.

5 STATISTICAL AND ANALYTICAL PLANS

5.1 Sample size determination

No formal sample size calculation has been performed for this study. The proposed sample size is considered sufficient to provide adequate information for the study objectives.

5.2 Definition of analysis sets

5.2.1 Full analysis set

The Full Analysis Set (FAS) will consist of all subjects who have been randomised and used at least one of the IPs and who has at least one post-baseline assessment of data.

5.2.2 Pharmacokinetic analysis set

The Pharmacokinetic analysis set (PKAS) will consist of all subjects who used at least one of the IPs and provided an evaluable plasma concentration profile and who have no AEs or protocol deviations judged to affect the PK analysis. Individual PK values may be excluded from the analysis as specified in the SAP. The PKAS will be used as the per protocol analysis set.

5.2.3 Use of analysis set

The use of the analysis sets/populations is indicated for each table/figure/listing under statistical output layout .

5.3 Definition of baseline

The baseline measurement is defined as the latest measurement prior to first IP exposure of each treatment period of the IP.

5.4 Output rounding principles

Generally, no rounding of data will be done prior to calculating statistics. However, if reported data contains more than 8 significant digits it will be rounded to 8 significant digits in the database.

In statistical output and descriptive summaries, the following principles will be followed:

- 3 significant digits will be used for PK and similar parameters.
- 2 significant digits will be used for percentages (for example relative change from baseline).
- p-values and similar statistical output will be presented using 4 decimal points.
- All descriptive summaries of numerical data (e.g. mean, SD etc.) will be presented with one extra decimal compared to reported input data.

CONFIDENTIAL

Document name: IB-OND-ZONEX-11_SAP_v1.0_23NOV2021

5.5 Significance level

When testing equivalence (as for the primary endpoint), a significance level of 10% will be used ($\alpha=0.10$). All other hypothesis testing (when not testing equivalence) will use a 5% significance level ($\alpha=0.05$).

5.6 Multiple comparisons/multiplicity

No adjustment for multiple comparison/multiplicity will be performed. All significant findings will be reviewed for medical relevance.

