### 11.4.3 *Product evaluation scale*

The subject will self-assess their experience of product effect using the PES [1] approximately 8 hours (after PK sampling) after the start of use of each IP, see Table 8.1-1. Each question will be answered using a Likert scale ranging from 1 to 7, where 1 corresponds to "not at all" and 7 to "extremely". The answers, provided using a paper questionnaire, will be entered in the eCRF by the study personnel.

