### 11.4.5 *Urge to use questionnaire*

The subject will self-assess their urge to use a nicotine pouch pre IP-use and at each PK sampling time point (after PK sampling).

Using a 100 mm visual analogue scale (VAS), with the anchor points 0 mm (= not at all/no urge) and 100 mm (= extremely/extreme urge), the subjects will answer the question: How strong is your urge to use a nicotine pouch right now?

The self-assessment for each question at each time point (in mm's) will be entered in the eCRF by the study personnel.

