8.1 Primary endpoint(s) analysis

8.1.1 C_{max} and AUC_t

This section refers to the primary objective 1, endpoint 1.1.

C_{max} and AUC_t and baseline adjusted C_{max} and AUC_t will be summarised descriptively. Also, log transformed nicotine C_{max} and AUC_t estimates will be evaluated separately in a linear mixed-effects analysis of variance model with fixed effects for product and a random effect for subject. The above product differences will be back-transformed to present the ratios of geometric least squares (LS) means coupled with the 90% confidence intervals (CIs). If the CI falls within the range of 0.8-1.25, the corresponding two products are considered equivalent with respect to that comparison.

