9 CHANGES FROM THE CSP

9.1 Changes of product comparisons for primary analysis

In the protocol (Synopsis and Section 17.5) it was stated that the primary objective will be examined by the following statistical comparisons for AUC and C_{max} :

- Product A versus Product B, C and D, respectively

CONFIDENTIAL

Document name: IB-OND-ZONEX-11_SAP_v1.0_23NOV2021

- Product B versus Product C and D, respectively
- Product C versus Product D

Instead, the primary objective will be examined by the following statistical comparisons for AUC_t and C_{max} :

- Product A does not significantly differ from Product D
- Product B does not significantly differ from Product D
- Product C does not significantly differ from Product D

The reason for the change is that the test products are Products A-C and the Comparator product is Product D, so there is no need for multiple comparisons.

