9.3 Change of analysis method for Urge to use questionnaire for secondary analysis

In the protocol it was stated that the same statistical method as described for the PK analysis will be used to compare Urge to use parameters. Instead, change from baseline will be evaluated descriptively for each IP.

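### SAP 5.6 drops the protocol's Bonferroni-Holm rule for urge to use without declaring it, Table 14.2.5 still orders unadjusted urge p-values, and SAP 8.1.1 has no product-level equivalence rule

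*SAP*

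**What the plan says.** **Multiplicity.** Protocol 17.1: "For subject questionnaires measured at each PK time point, the Bonferroni-Holm p-value adjustment will be applied". SAP 5.6: "No adjustment for multiple comparison/multiplicity will be performed". SAP 5.6 adds only that significant findings will be reviewed for medical relevance.

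**Where changes are recorded.** SAP 3: "Any changes from the final CSP are given in Section 9". Section 9 has three entries: product comparisons (9.1), fixed effects (9.2) and the urge-to-use method (9.3). The one remark there that touches multiplicity is in 9.1, on the reduction to three contrasts with D: "so there is no need for multiple comparisons".

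**Urge to use.** SAP 9.3 withdraws the model-based comparison that the protocol planned: "Instead, change from baseline will be evaluated descriptively for each IP". SAP 8.2.2 nevertheless lists Table 14.2.5 as a table of treatment comparisons. Its shell has rows for A, B and C against D, 90% confidence limits and a p-value column.

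**Primary endpoints.** SAP 8.1.1 compares each 90% confidence interval with 0.8-1.25. If it lies inside, "the corresponding two products are considered equivalent with respect to that comparison". The primary objective (Protocol 7.1, SAP 4.1) names Cmax and AUCt together.

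**The concern.** A prespecified error-control rule has disappeared, and someone who relies on Section 9 to learn what changed would not find out. The loss has a practical effect only if urge-to-use p-values are still produced. Section 9.3 says they will not be, and the output shells say they will. If the shell is programmed as it stands, the report will carry p-values for the one questionnaire the protocol protected, without that protection.

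The primary analysis has a related gap. Six verdicts are issued one at a time, and nothing says what a product must achieve before it is called equivalent to the comparator. A product could pass on AUCt and fail on Cmax, and the SAP gives the report's author no rule for describing it.

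**Working it through.** The plan states no familywise error rate, power or sample size calculation, so there is no figure of its own to reproduce.

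**1. What the protocol's Holm sentence covers.** It applies to questionnaires measured at each PK time point.

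- Urge to use: before use and at every PK sampling time (Protocol 11.4.5). Covered.
- PES: once per product, "approximately 8 hours (after PK sampling) after the start of use of each IP" (Protocol 11.4.3). Not covered.
- PPS: once, on Day 4 (Protocol 11.4.4). Not covered.

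**2. What is declared.** Sections 9.1 and 9.2 concern the PK model. Section 9.3 changes the urge-to-use method and does not mention Holm. The removal is therefore undeclared.

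**3. Urge p-values still ordered.** The Table 14.2.5 shell names Emax and TEmax and continues with an ellipsis. Assuming the ellipsis stands for AUEC0-120, the third derived parameter in SAP 8.2.1.5:

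- p-values: 3 parameters × 3 contrasts = 9
- chance of at least one false p < 0.05, if independent: 1 − 0.95^9 = 37% (the true figure depends on correlations the documents do not give)
- first Holm threshold: 0.05/9 = 0.0056

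These are derived parameters rather than scores at single time points. They are, however, the only urge comparisons Protocol 17.6.5 describes, so they are what its Holm rule would most naturally act on.

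**4. Equivalence verdicts.** 3 products × 2 parameters = 6. A 90% interval inside the limits corresponds to two one-sided tests at 0.05 each (z = 1.645).

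- At least one false verdict, if independent: 1 − 0.95^6 = 26.5%
- Three product-level decisions, each at most 0.05: sum 0.15; if independent, 1 − 0.95^3 = 14.3%

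The contrasts share D, and the two parameters are correlated, so the rates were also simulated: four-product crossover, n = 27, normal log-scale data, all true ratios at 1.25. The within-subject CV of 20% and the correlations are assumptions.

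| Correlation of Cmax and AUCt | At least one of six verdicts false | Any product falsely passing both |
|---|---|---|
| 0 | 22% | 0.7% |
| 0.5 | 20% | 3% |
| 0.8 | 17% | 6% |

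Requiring both parameters is an intersection-union rule: each test stays at its own level, and the false-label rate per product cannot exceed 5%. The last column assumes both parameters sit at the limit. If only one does and the other is comfortably equivalent, the rate per product can approach 5%, and the total across products is bounded by 15%.

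**5. PES, for scale.** SAP 8.2.1.3 tests four subscales and the total, and the Table 14.2.2 shell sets A, B and C against D: 5 × 3 = 15 p-values at 0.05. If independent, the chance of at least one false finding is 1 − 0.95^15 = 54%. Simulation under the null with the shared reference D gives:

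| Assumed correlation | Five exchangeable scores | Total built as the sum of the subscales |
|---|---|---|
| 0 | 49% | 45% |
| 0.5 | 41% | 36% |
| 0.7 | 34% | 30% |

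These rates assume correctly sized paired tests. Protocol 17.6.3 names a signed-rank test and SAP 8.2.1.3 a rank-sum test. An unpaired rank-sum test on within-subject data would be conservative: simulated familywise error was about 18-24%, 9-11% and 1-2% for assumed within-subject correlations of 0.3, 0.5 and 0.7.

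**The case against.** The strongest reply is that Section 9.3 does the work. Once urge to use is descriptive, Holm has nothing to adjust, and its removal merely follows from a declared change. That would be a full answer if the outputs agreed. They do not, because SAP 8.2.2 and the shell keep the comparisons. The shell may simply be left over: it has the layout of the PK comparison table (ratios of geometric LS means, 90% limits) and a footnote naming the PK analysis set under a title naming the full analysis set. That is plausible, but a programmer works from the shells.

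On the primary side, SAP 8.1.1 already confines each verdict to its own comparison, and no passage lets one parameter establish product equivalence. That stands. A reader might infer that the SAP permits such a claim, but it only leaves the question open.

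Two further readings go beyond the documents. A reader might infer that the SAP cancelled an adjustment of the PES p-values. It did not, since PES is taken once per product and was never under the rule. A reader might also conclude that a spurious PES difference is more likely than not. The simulated rates are all below one half, and items 17, 19 and 21 are summarised without tests. In a Phase I study with no sample size calculation, unadjusted p-values on a secondary scale are defensible if labelled as such.

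**Conclusion.** The point stands in two parts.

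First, SAP 5.6 departs from Protocol 17.1 for urge to use without an entry in Section 9, and Table 14.2.5 contradicts Section 9.3. This rests on the text alone. Its size is nine unadjusted p-values, given the reading of the ellipsis above, or none if 9.3 governs.

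Second, the SAP has no product-level equivalence rule. At the 1.25 limit, requiring both parameters replaces a 17-22% chance of some false single-parameter verdict with a 1-6% chance of a false product label. This assumes a 20% CV and correlations of 0 to 0.8. The two rates describe different claims, and the gain lies in making the product label the claim that is controlled.

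The PES p-values are a lesser matter of labelling. The chance of at least one false finding is about 30-49% for assumed score correlations of 0 to 0.7 and correctly sized paired tests, and it is lower if the unpaired test is run as written. None of this invalidates the planned estimates or intervals.

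**What to change.** 1. **Urge to use.** Reconcile Table 14.2.5 with SAP 9.3. Either delete the treatment comparisons and p-values from the shell and from the list in 8.2.2, or keep them, correct 9.3, and apply Holm across them as Protocol 17.1 requires. Declare and justify in Section 9 any remaining departure from 17.1, and make 5.6 agree. Cost: wording, plus one PROC MULTTEST step if the p-values stay, which would then be larger.
2. **Equivalence.** In SAP 8.1.1, state that a product is called equivalent to D only if the 90% confidence intervals for both Cmax and AUCt lie within 0.8-1.25. Report single-parameter results as ratios and intervals without that label. No alpha penalty is needed. The cost is fewer equivalence labels.
3. **PES (optional).** Label the 15 p-values exploratory in 5.6 and Table 14.2.2, or adjust them. Holm here would be a new rule, with a first threshold of 0.05/15 = 0.0033, and should be presented as such.

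No change requires new data.
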